9.14.5 Ocular Events

An ophthalmologist should evaluate visual complaints (e.g., uveitis, retinal events).

Table 9-7 Management Guidelines for Ocular Events

Severity	Management
Grade 1	
Continue atezolizumabEvaluation by an ophthalmologist is strongly recommendedTreat with topical corticosteroid eye drops and topical immunosuppressive therapyIf symptoms persist, treat as a Grade 2 event
Grade 2	
Withhold atezolizumab for up to 12 weeks after event onset ^aPatient referral to ophthalmologist is strongly recommendedStart treatment with topical corticosteroid eye drops and topical immunosuppressive therapyIf event resolves to Grade 0 or Grade 1, resume atezolizumab ^bIf event does not resolve to Grade 0 or Grade 1 or better while withholding atezolizumab, permanently discontinue atezolizumab and contact Medical Monitor ^c
Grade 3 or 4	
Permanently discontinue atezolizumab and contact Medical Monitor ^cRefer patient to ophthalmologistInitiate treatment with 1–2 mg/kg/day oral prednisone or equivalentIf event resolves to Grade 0 or Grade 1, taper corticosteroids over \geq 1 month

^a Atezolizumab may be withheld for a longer period of time (i.e., >12 weeks after event onset) to allow for corticosteroids (if initiated) to be reduced to ≤ 10 mg/day oral prednisone or equivalent. The acceptable length of the extended period of time must be agreed upon by the investigator and the Medical Monitor.

^b If corticosteroids have been initiated, they must be tapered over ≥ 1 month to ≤ 10 mg/day oral prednisone or equivalent before atezolizumab can be resumed.

^c Resumption of atezolizumab may be considered in patients who are deriving benefit and have fully recovered from the immune-related event. Patients can be rechallenged with atezolizumab only after approval has been documented by both the investigator (or an appropriate delegate) and the Medical Monitor.

9.14.6 Immune-Related Myocarditis

Immune-related myocarditis has been associated with the administration of atezolizumab. Immune-related myocarditis should be suspected in any patient presenting with signs or symptoms suggestive of myocarditis, including, but not limited to, dyspnea, chest pain, palpitations, fatigue, decreased exercise tolerance, or syncope. Immune-related myocarditis needs to be distinguished from myocarditis resulting from infection (commonly viral, e.g. in a patient who reports a recent history of gastrointestinal illness), ischemic events, underlying arrhythmias, exacerbation of pre-existing cardiac conditions, or progression of malignancy.

All patients with possible myocarditis should be urgently evaluated by performing cardiac enzyme assessment, an ECG, a chest X-ray, an echocardiogram, and a cardiac MRI as appropriate per institutional guidelines. A cardiologist should be consulted. An endomyocardial biopsy may be considered to enable a definitive diagnosis and appropriate treatment, if clinically indicated.

Table 9-8 Management Guidelines for Immune-Related Myocarditis

Severity	Management
Grade 1	
Refer patient to cardiologistStart treatment as per institutional guidelines
Grade 2	
Withhold atezolizumab for up to 12 weeks after event onset^a and contact Medical MonitorRefer patient to cardiologistInitiate treatment as per institutional guidelines and consider antiarrhythmic drugs, temporary pacemaker, ECMO, or VAD as appropriateConsider treatment with 1–2 mg/kg/day IV methylprednisolone or equivalent and convert to 1–2 mg/kg/day oral prednisone or equivalent upon improvement^aIf event resolves to Grade 0 or Grade 1, resume atezolizumab^bIf event does not resolve to Grade 0 or Grade 1 while withholding atezolizumab, permanently discontinue atezolizumab and contact Medical Monitor^c
Grade 3-4	
Permanently discontinue atezolizumab and contact Medical Monitor^cRefer patient to cardiologistInitiate treatment as per institutional guidelines and consider antiarrhythmic drugs, temporary pacemaker, ECMO, or VAD as appropriateInitiate treatment with 1–2 mg/kg/day IV methylprednisolone or equivalent and convert to 1–2 mg/kg/day oral prednisone or equivalent upon improvement^{a,b}If event does not improve within 48 hours after initiating corticosteroids, consider adding an immunosuppressive agentIf event resolves to Grade 0 or Grade 1, taper corticosteroids over \geq 1 month

ECMO = extracorporeal membrane oxygenation; VAD = ventricular assist device;

IV = intravenous.

^a Atezolizumab may be withheld for a longer period of time (i.e., > 12 weeks after event onset) to allow for corticosteroids (if initiated) to be reduced to ≤ 10 mg/day oral prednisone or equivalent. The acceptable length of the extended period of time must be agreed upon by the investigator and the Medical Monitor.

^b If corticosteroids have been initiated, they must be tapered over ≥ 1 month to ≤ 10 mg/day oral prednisone or equivalent before atezolizumab can be resumed.

^c Resumption of atezolizumab may be considered in patients who are deriving benefit and have fully recovered from the immune-related event. Patients can be rechallenged with atezolizumab only after approval has been documented by both the investigator (or an appropriate delegate) and the Medical Monitor.

9.14.7 Pancreatic Events

Symptoms of abdominal pain associated with elevations of amylase and lipase, suggestive of pancreatitis, have been associated with the administration of other immuno-modulatory agents. The differential diagnosis of acute abdominal pain should include pancreatitis. Appropriate work-up should include an evaluation for ductal obstruction, as well as serum amylase and lipase tests.

Table 9-9 Management Guidelines for Pancreatitis

Pancreatic Event	Severity	Management
Amylase and /or lipase elevation	Grade 2	
 Continue atezolizumab Monitor amylase/lipase weekly Consider oral prednisone 10 mg daily or equivalent for prolonged elevation (e.g., more than 3 weeks)
Amylase and /or lipase elevation	Grades 3 and 4	
 Withhold atezolizumab for up to 12 weeks after event onset ^a Consult a gastroenterologist Monitor amylase/lipase every other day Consider oral prednisone 1-2 mg/kg/day or equivalent if no improvement Atezolizumab may be resumed if the event resolves to Grade 0 or Grade 1 ^b If event does not resolve to Grade 0 or Grade 1 while withholding atezolizumab, permanently discontinue atezolizumab and contact Medical Monitor ^c Permanently discontinue atezolizumab for recurrent events and notify the Medical Monitor ^c
Immune-related pancreatitis	Grade 2 or 3	
 Withhold atezolizumab for up to 12 weeks after event onset ^a Consult a gastroenterologist Start treatment with 1-2 mg/kg/day IV methylprednisolone or equivalent and convert to 1-2 mg/kg/day oral prednisone or equivalent when symptoms improve Atezolizumab may be resumed if the event improves to Grade 0 or Grade 1 If event does not resolve to Grade 1 or better while withholding atezolizumab, permanently discontinue atezolizumab and contact Medical Monitor ^c Permanently discontinue atezolizumab for recurrent events and notify the Medical Monitor ^c
Immune-related pancreatitis	Grade 4	
 Permanently discontinue atezolizumab and contact Medical Monitor ^c Refer patient to gastrointestinal specialist Start treatment with 1-2 mg/kg/day IV methylprednisolone or equivalent and convert to 1-2 mg/kg/day oral prednisone or equivalent upon improvement If event does not improve within 48 hours after initiating corticosteroids, consider adding an immunosuppressive agent If event resolves to Grade 0 or Grade 1, taper corticosteroids over \geq 1 month.

IV=intravenous;

^a Atezolizumab may be withheld for a longer period of time (i.e., >12 weeks after event onset) to allow for corticosteroids (if initiated) to be reduced to \leq 10 mg/day oral prednisone or equivalent. The acceptable length of the extended period of time must be agreed upon by the investigator and the Medical Monitor.

- ^b If corticosteroids have been initiated, they must be tapered over ≥ 1 month to ≤ 10 mg/day oral prednisone or equivalent before atezolizumab can be resumed.
- ^c Resumption of atezolizumab may be considered in patients who are deriving benefit and have fully recovered from the immune-related event. Patients can be rechallenged with atezolizumab only after approval has been documented by both the investigator (or an appropriate delegate) and the Medical Monitor.

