Asymptomatic hypothyroidism	
 Continue atezolizumab Start thyroid replacement hormone Monitor TSH weekly
Symptomatic hypothyroidism	
 Withhold atezolizumab. Start thyroid replacement hormone Monitor TSH weekly Consider referral to an endocrinologist. Restart atezolizumab when symptoms are controlled and thyroid function is improving
Asymptomatic hyperthyroidism	
If serum TSH ≥ 0.1 mU/L and < 0.5 mU/L:
 
 Continue atezolizumab. Monitor TSH every 4 weeks 
TSH < 0.1 mU/L:
 
Follow guidelines for symptomatic hyperthyroidism

Symptomatic hyperthyroidism	
 Withhold atezolizumab Initiate treatment with anti-thyroid drug such as methimazole or carbimazole as needed Consider referral to an endocrinologist Restart atezolizumab when symptoms are controlled by thyroid replacement and thyroid function is improving Permanently discontinue atezolizumab and contact Medical Monitor for life-threatening immune-related hyperthyroidism ^c
Symptomatic adrenal insufficiency, Grade 2–4	
 Withhold atezolizumab for up to 12 weeks after event onset ^a Refer patient to endocrinologist Perform appropriate imaging Initiate treatment with 1–2 mg/kg/day IV methylprednisolone or equivalent and convert to 1–2 mg/kg/day oral prednisone or equivalent upon improvement If event resolves to Grade 0 or Grade 1 and patient is stable on replacement therapy, resume atezolizumab ^b If event does not resolve to Grade 0 or Grade 1 or patient is not stable on replacement therapy while withholding atezolizumab, permanently discontinue atezolizumab and contact Medical Monitor ^c
Hyperglycemia Grade 1 or 2	
 Continue atezolizumab Start treatment with insulin if needed Monitor for glucose control

Table 9-6 Management Guidelines for Endocrine Events

Hyperglycemia, Grade 3 or 4	
 Withhold atezolizumab Start treatment with insulin Monitor for glucose control Resume atezolizumab when symptoms resolve and glucose levels are stable

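### Grade 2 or 3 immune-related pancreatitis is the only row naming systemic steroids from which atezolizumab may restart without the steroid-taper condition

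*Protocol*

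**What the plan says.** Table 9-9 in protocol section 9.14.7 covers two kinds of pancreatic event: raised amylase or lipase, and immune-related pancreatitis. For pancreatitis of Grade 2 or 3, the row withholds atezolizumab for up to 12 weeks and asks for a gastroenterology consult. It starts IV methylprednisolone at 1-2 mg/kg/day, with conversion to 1-2 mg/kg/day "oral prednisone or equivalent when symptoms improve". On restarting, it says only "Atezolizumab may be resumed if the event improves to Grade 0 or Grade 1". Footnotes a and c are marked in this row; footnote b is not.

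In the same table, the row for Grade 3 and 4 amylase or lipase elevation does carry it: "Atezolizumab may be resumed if the event resolves to Grade 0 or Grade 1 ^b". Footnote b, printed below the table, says of any steroids already started that "they must be tapered over ≥ 1 month to ≤ 10 mg/day oral prednisone or equivalent before atezolizumab can be resumed". Footnote a begins "Atezolizumab may be withheld for a longer period of time" and lets the hold run past 12 weeks, by agreement with the Medical Monitor, so that steroids can come down to 10 mg/day or less.

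Table 9-11, in section 9.14.8, reprints the pancreatic guidance. Its Grade 2 or 3 pancreatitis row also lacks footnote b.

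**The concern.** Footnotes in these tables are assigned row by row through their markers. A row that starts high-dose steroids and allows restart without marker b therefore reads as having no steroid condition. A site taking the row literally could give atezolizumab again as soon as pancreatitis reaches Grade 0 or 1, with the patient still on a high steroid dose. A site that applies footnote b to the whole table would wait for the taper.

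Pancreatitis is an adverse event of special interest under section 12.4.3. The risk is re-exposure while the event is held down by steroid rather than resolved. In addition, section 9.12 warns that systemic corticosteroids may blunt the benefit of atezolizumab.

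The ordering within the table is also odd. The laboratory abnormality, where prednisone is only to be considered, has the taper condition. The clinical event, where IV steroids are directed, does not.

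**Working it through.** The check is a count of rows, with one short dose calculation.

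**Rule for counting.** Include every distinct row of section 9.14 that withholds atezolizumab and then allows restart. Table 9-11 is treated as a copy of Table 9-9. The Grade 2 infusion reaction in Table 9-10 is left out because it interrupts and resumes the same infusion. Rows that permanently discontinue, with case-by-case rechallenge under footnote c, are also left out. Asymptomatic hyperthyroidism with TSH below 0.1 mU/L refers to the symptomatic row and is not counted again.

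| Row | Systemic steroid named | Taper in the row's own bullets | Footnote b on restart |
|---|---|---|---|
| 9-3 pulmonary, Grade 2 | oral | yes | yes |
| 9-4 hepatic, Grade 2 | oral | yes | yes |
| 9-5 gastrointestinal, Grade 2 | oral, if persistent or recurrent | yes | yes |
| 9-5 gastrointestinal, Grade 3 | IV then oral | yes | yes |
| 9-6 adrenal insufficiency, Grade 2-4 | IV then oral | no | yes |
| 9-6 hypophysitis, Grade 2-3 | IV then oral | no | yes |
| 9-7 ocular, Grade 2 | none (topical only) | no | yes |
| 9-8 myocarditis, Grade 2 | IV then oral (consider) | no | yes |
| 9-9 amylase/lipase, Grade 3-4 | oral (consider) | no | yes |
| **9-9 pancreatitis, Grade 2-3** | **IV then oral** | **no** | **no** |
| 9-12 dermatologic, Grade 3 | oral | no | yes |
| 9-13 neuropathy, Grade 2 | none named | no | yes |
| 9-6 symptomatic hypothyroidism | none | no | no |
| 9-6 symptomatic hyperthyroidism | none | no | no |
| 9-6 hyperglycemia, Grade 3-4 | none | no | no |

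**Counts.**
- All withhold-and-restart rows: 12 with a 12-week limit + 3 without = 15. Footnote b is on 11 and absent from 4.
- Three of those 4 start no steroid. Their restart wording is "Restart atezolizumab when symptoms are controlled and thyroid function is improving" (hypothyroidism), "Restart atezolizumab when symptoms are controlled by thyroid replacement and thyroid function is improving" (hyperthyroidism) and "Resume atezolizumab when symptoms resolve and glucose levels are stable" (hyperglycemia). A taper condition would have nothing to act on there.
- Rows with the 12-week limit: b on 11 of 12.
- Rows naming systemic steroids: 12 - 2 (ocular, neuropathy) = 10, with b on 9.
- Rows naming IV methylprednisolone 1-2 mg/kg/day: 5, with b on 4.
- Steroid rows with no taper bullet of their own: 10 - 4 = 6, with b on 5. The missing taper bullet is therefore not unusual in itself. What is unique to the pancreatitis row is having neither the bullet nor the footnote.

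Table 9-11 differs from Table 9-9 in one place: its amylase/lipase row gains a taper bullet. The pancreatitis row is unchanged.

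**Dose against the ceiling.** Section 5.3.2 equates 1200 mg with 15 mg/kg, so the implied weight is 1200 / 15 = 80 kg. Oral prednisone at 1-2 mg/kg/day is then 80 x 1 = 80 to 80 x 2 = 160 mg/day. Divided by footnote b's 10 mg/day, that is 8 to 16 times the ceiling. Over an assumed weight range of 50 to 100 kg, the dose runs from 50 x 1 = 50 to 100 x 2 = 200 mg/day, or 5 to 20 times.

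These multiples describe the treatment dose, the only one the row states. They do not estimate the dose at restart. No number of affected infusions can be given, because footnote b sets a minimum taper, not a fixed one.

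**The case against.** The strongest reply is that the rule is already on the page. Footnote b is printed under the same table, is mandatory, names no event or grade, and fits this row exactly because the row directs steroids. Footnote a, which is on the row, only makes sense if 10 mg/day is the target before restart, and section 9.10.2 uses the same target. On this view a superscript is missing but the content is not.

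There are other safeguards. Resumption is optional. The row requires a gastroenterology consult and permanent discontinuation on recurrence. Section 9.10 lets investigators be more conservative than the guidelines. Section 9.14 asks for a benefit-risk judgement before further dosing, and section 12.4.3 requires a check for events of special interest before each dose.

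Much of this stands. It makes the intent fairly clear and an unnoticed early restart less likely. It also supports reading the omission as a drafting slip rather than a deliberate rule for pancreatitis. But footnote a and section 9.10.2 only permit a longer hold, and none of the other safeguards sets a steroid level before restart. The 10 mg or 7-day steroid limits in section 9.12 do not help, since they apply to conditions other than immune-mediated toxicity from study drug. The protocol otherwise relies on marker b, and places it even on the ocular and neuropathy rows, where no systemic steroid is named. Its absence here therefore leaves room for two readings.

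The objection that the dose multiples do not measure the likely deviation is fair, and they are given with that limit. Loss of the marker in text extraction is possible but unlikely: the row's a and c markers survive, and b is missing from both copies.

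**Conclusion.** The concern holds. As written, the row permits a restart that the protocol bars in each of the other nine rows naming systemic steroids, and no other text attaches a steroid condition to it. The finding rests on reading footnotes as applying where they are marked, and on the absence of b in both printed copies being real.

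The consequence is small. It is a patient-safety consistency correction that would affect the few patients with Grade 2 or 3 immune-related pancreatitis who are considered for restart. No sample size, power or efficacy figure depends on it. Confidence is high about the missing marker. How sites would act on it cannot be known from the documents.

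**What to change.** Add footnote marker b to the resumption bullet of the Grade 2 or 3 immune-related pancreatitis row in Table 9-9, and in Table 9-11 for as long as that copy is printed. Footnote b would then be on 10 of 10 rows naming systemic steroids.

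The cost is one superscript per copy at the next amendment, and a somewhat longer atezolizumab hold for the patients concerned. Footnote a already lets the hold run past 12 weeks with the agreement of the investigator and Medical Monitor, so completing the taper need not force discontinuation. Removing the duplicate table would be a separate editorial matter.

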9.14.8 Infusion-Related Events

No premedication is indicated for the administration of atezolizumab in Cycle 1. Patients who experience an infusion-related reaction with Cycle 1 of atezolizumab may receive premedication with antihistamines or antipyretics/analgesics (e.g., acetaminophen) for subsequent infusions. Metamizole (dipyrone) is prohibited in treating atezolizumab associated infusion-related reactions, due to its potential for causing agranulocytosis.

Table 9-10 Management Guidelines for Infusion-Related Reactions

Severity	Management
Grade 1	
Reduce infusion rate to half the rate being given at the time of event onsetAfter the event has resolved, the investigator should wait for 30 minutes while delivering the infusion at the reduced rateIf tolerated, the infusion rate may then be increased to the original rate
Grade 2	
Interrupt atezolizumab infusionAdminister aggressive symptomatic treatment (e.g., oral or IV antihistamine, anti-pyretic, glucocorticoids, epinephrine, bronchodilators, oxygen)After symptoms have resolved to baseline, resume infusion at half the rate being given at the time of event onset
For subsequent infusions, consider administration of oral premedication with antihistamine, anti-pyretics, and/or analgesics and monitor closely for IRRs
Grades 3–4	
Stop infusionAdminister aggressive symptomatic treatment (e.g., oral or IV antihistamine, anti-pyretic, glucocorticoids, epinephrine, bronchodilators, oxygen)Permanently discontinue atezolizumab and contact Medical Monitor ^a

IRR=infusion-related reactions; IV=intravenous.

^aResumption of atezolizumab may be considered in patients who are deriving benefit and have fully recovered from the immune-related event. Patients can be rechallenged with atezolizumab only after approval has been documented by both the investigator (or an appropriate delegate) and the Medical Monitor.

Table 9-11 Management Guidelines for Pancreatitis

Pancreatic Event	Severity	Management
Amylase and /or lipase elevation	Grade 2	
Continue atezolizumabMonitor amylase/lipase weeklyConsider oral prednisone 10 mg daily or equivalent for prolonged elevation (e.g., more than 3 weeks)

Amylase and /or lipase elevation	Grades 3 and 4	
 Withhold atezolizumab for up to 12 weeks after event onset ^a Consult a gastroenterologist Monitor amylase/lipase every other day Consider oral prednisone 1-2 mg/kg/day or equivalent if no improvement When lab abnormalities return to Grade 0 or Grade 1, then taper steroids over ≥ 1 month Atezolizumab may be resumed if the event resolves to Grade 0 or Grade 1 ^b If event does not resolve to Grade 0 or Grade 1 while withholding atezolizumab, permanently discontinue atezolizumab and contact Medical Monitor ^c Permanently discontinue atezolizumab for recurrent events and notify the Medical Monitor ^c
Immune-related pancreatitis	Grade 2 or 3	
 Withhold atezolizumab for up to 12 weeks after event onset ^a Consult a gastroenterologist Start treatment with 1-2 mg/kg/day IV methylprednisolone or equivalent and convert to 1-2 mg/kg/day oral prednisone or equivalent when symptoms improve Atezolizumab may be resumed if the event improves to Grade 0 or Grade 1 If event does not resolve to Grade 1 or better while withholding atezolizumab, permanently discontinue atezolizumab and contact Medical Monitor ^c Permanently discontinue atezolizumab for recurrent events and notify the Medical Monitor ^c
Immune-related pancreatitis	Grade 4	
 Permanently discontinue atezolizumab and contact Medical Monitor ^c Refer patient to gastrointestinal specialist Start treatment with 1-2 mg/kg/day IV methylprednisolone or equivalent and convert to 1-2 mg/kg/day oral prednisone or equivalent upon improvement If event does not improve within 48 hours after initiating corticosteroids, consider adding an immunosuppressive agent If event resolves to Grade 0 or Grade 1, taper corticosteroids over ≥ 1 month.

IV=intravenous;

^a Atezolizumab may be withheld for a longer period of time (i.e., > 12 weeks after event onset) to allow for corticosteroids (if initiated) to be reduced to ≤ 10 mg/day oral prednisone or equivalent. The acceptable length of the extended period of time must be agreed upon by the investigator and the Medical Monitor.

^b If corticosteroids have been initiated, they must be tapered over ≥ 1 month to ≤ 10 mg/day oral prednisone or equivalent before atezolizumab can be resumed.

^c Resumption of atezolizumab may be considered in patients who are deriving benefit and have fully recovered from the immune-related event. Patients can be rechallenged with atezolizumab only after approval has been documented by both the investigator (or an appropriate delegate) and the Medical Monitor.

9.14.9 Dermatologic Events

Treatment-emergent rash has been associated with atezolizumab. The majority of cases of rash were mild in severity and self-limited, with or without pruritus. A dermatologist should evaluate persistent and/or severe rash or pruritus. A biopsy should be considered unless contraindicated.

Table 9-12 Management Guidelines for Immune-Mediated Dermatologic Events

Severity	Management
Grade 1	
Continue atezolizumabConsider topical corticosteroids and/or other symptomatic therapy (e.g., antihistamines)
Grade 2	
Continue atezolizumabConsider dermatologist referralAdminister topical corticosteroidsConsider higher potency topical corticosteroids if event does not improve
Grade 3	
Withhold atezolizumab for up to 12 weeks after event onset ^aConsult a dermatologistStart treatment with oral prednisone 10 mg/day or equivalent. If event unresolved after 48–72 hours, administer oral prednisone 1-2 mg/kg/day or equivalentRestart atezolizumab if event resolves to Grade 0 or Grade 1 ^bIf event does not resolve to Grade 0 or Grade 1 while withholding atezolizumab, permanently discontinue atezolizumab and contact Medical Monitor ^c
Grade 4	
Permanently discontinue atezolizumab and contact Medical Monitor ^c

^a Atezolizumab may be withheld for a longer period of time (i.e., > 12 weeks after event onset) to allow for corticosteroids (if initiated) to be reduced to \leq 10 mg/day oral prednisone or equivalent. The acceptable length of the extended period of time must be agreed upon by the investigator and the Medical Monitor.

^b If corticosteroids have been initiated, they must be tapered over \geq 1 month to \leq 10 mg/day oral prednisone or equivalent before atezolizumab can be resumed.

^c Resumption of atezolizumab may be considered in patients who are deriving benefit and have fully recovered from the immune-related event. Patients can be rechallenged with atezolizumab only after approval has been documented by both the investigator (or an appropriate delegate) and the Medical Monitor.

